2.3 Correlative Research

- 2.31 To correlate tumor response (RECIST 1.1) with pretreatment frequency of CD8⁺ T cells in the primary and/or metastatic tumor. FFPE tumor samples will be evaluated for CD8⁺ T cells by immunohistochemistry. Staining intensity is scored on a 1⁺ to 3⁺ scale, and the percentage of positive cells per total lymphocytes is estimated (1 = <1%, 2 = 1-10%, 3 = 11-33%, 4 = 34-66%, 5 = 67-100%). Allred scores (intensity + percent positive) are generated for comparison between samples (Phillips T, et. al., 2007). Quantitation of the CD8⁺ cells will be performed using the Aperio Scanscope AT2 system (20X, 0.5 μm/pixel resolution). Our collaborating pathologist will designate both peritumoral and intratumoral areas for differential quantitation using the Aperio ImageScope application, and annotated regions will be analyzed for positive staining using an Aperio colormetric thresholding algorithm. To extrapolate the number of positive cells per mm², 15 random cells will be chosen to determine the average pixels per positive CD8 event. The average number of CD8 pixels will be divided by the total positive pixels to determine the number of positive CD8 cells in the annotated regions. The number of CD8 cells divided by the area will estimate the number of positive cells per mm². (Cohort 1 and 2)
- 2.32 To correlate tumor response (RECIST 1.1) with pretreatment PD-L1 and PD-L2 levels in the primary and/or metastatic tumor. Tumors will be evaluated for PD-L1 (by QualTek Clinical Laboratories) and anti-PD-L2 (Biogen M1H18) by immunohistochemistry, as described above. (Cohort 1 and 2)
- 2.33 To correlate tumor response (RECIST 1.1) with pretreatment frequency of lymphocytes expressing CD3, CD4, PD-1, FoxP3, or CD20, and of CD163⁺

macrophages. Cells types will be detected in pretreatment FFPE tumor tissue by immunohistochemistry. (Cohort 1 and 2)

- 2.34 To correlate tumor response (RECIST 1.1) with the phenotype and frequency of key leukocyte subsets (i.e., PD-1+ T cells, Tregs, myeloid subsets) in the peripheral blood before, at 6 and 18 weeks on therapy, and at 54 weeks (study completion), PD, or study withdrawal. Peripheral blood mononuclear cells and neutrophils will be isolated concomitantly by density gradient from peripheral blood, cryopreserved, and analyzed by 10-color flow cytometry. (Cohort 1)

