11.4 Measurement of Effect

11.41 Target Lesions & Target Lymph Nodes

- Measurable lesions (as defined in Section 11.21) up to a maximum of 5 lesions, representative of all involved organs, should be identified as “Target Lesions” and recorded and measured at baseline. These lesions can be non-nodal or nodal (as defined in 11.21), where no more than 2 lesions are from the same organ and no more than 2 malignant nodal lesions are selected.

Note: If fewer than 5 target lesions and target lymph nodes are identified (as there often will be), there is no reason to perform additional studies beyond those specified in the protocol to discover new lesions.

- Target lesions and target lymph nodes should be selected on the basis of their size, be representative of all involved sites of disease, but in addition should be those that lend themselves to reproducible repeated measurements. It may be the case that, on occasion, the largest lesion (or malignant lymph node) does not lend itself to reproducible measurements in which circumstance the next largest lesion (or malignant lymph node) which can be measured reproducibly should be selected.
- Baseline Sum of Dimensions (BSD): A sum of the longest diameter for all target lesions plus the sum of the short axis of all the target lymph nodes will be calculated and reported as the baseline sum of dimensions (BSD). The BSD will be used as reference to further characterize any objective tumor response in the measurable dimension of the disease.
- Post-Baseline Sum of the Dimensions (PBSD): A sum of the longest diameter for all target lesions plus the sum of the short axis of all the target lymph nodes will be calculated and reported as the post-baseline sum of dimensions (PBSD). If the radiologist is able to provide an actual measure for the target lesion (or target lymph node), that should be recorded, even if it is below 0.5 cm. If the target lesion (or target lymph node) is believed to be present and is faintly seen but too small to measure, a default value of 0.5 cm should be assigned. If it is the opinion of the radiologist that the target lesion or target lymph node has likely disappeared, the measurement should be recorded as 0 cm.
- The minimum sum of the dimensions (MSD) is the minimum of the BSD and the PBSD.

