16.2 Sample Size/Accrual Rate

16.21 Sample Size: A total of 25 evaluable Cohort 1 and 25 evaluable Cohort 2 patients will be accrued per study design (50 evaluable total), unless one or both cohorts of the study are permanently closed at the stage 1 analysis or undue

toxicity is observed. We anticipate accruing an additional 10 patients (5 Cohort 1, 5 Cohort 2) in order to account for ineligibility, cancellation, major treatment violation, or other reasons. Therefore, maximum accrual is 60 patients for this trial (30 for each Cohort).

16.22 Accrual Time and Study Duration: We expect to accrue about 3 patients per month to this trial. Therefore, the accrual period for this Phase II study is expected to be about 20 months. We anticipate that the study will take approximately 3 years to complete. This allows a 6 month follow-up for the final patient enrolled, along with data entry, data clean-up, and analysis.

16.3 Analysis of Secondary Endpoints for both Cohorts.

This study will assess multiple secondary endpoints, including adverse events, progression-free survival (PFS) and overall survival (OS). All these analyses will be done for each cohort separately. In addition, all primary/secondary data will be summarized by descriptive factors as well (i.e. prior treatment, etc.).

16.31 Adverse Events: All patients that have initiated treatment will be considered evaluable for assessing adverse events. The maximum grade for each type of adverse event will be recorded for each patient, and frequency tables will be reviewed to determine adverse event patterns. Only the grade 2+ adverse events will be assessed, regardless of relationship to the study treatment.

16.32 Progression-Free Survival (PFS): Defined as the time from registration to the first of either death due to any cause or progression. The distribution of PFS will be estimated using the method of Kaplan-Meier.

16.33 Overall Survival: Defined as the time from registration to death due to any cause. The distribution of survival time will be estimated using the method of Kaplan-Meier. Special attention will be paid to any registered patient who dies early (i.e., within 60 days) of initiating their treatment. Circumstances surrounding such early deaths will be classified as being either due to malignant disease, toxicity, other causes, or of unknown reasons.

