16.4 Laboratory Correlative Studies (all done by Cohort): All analyses with respect to the translational component of this study are intended to be hypothesis-generating and descriptive in manner. Clinical data (i.e. CR rates confirmed response rates, PFS, OS, etc.) will be correlated with tumor marker data of interest (CD8+, PD-L1, PD-L2, T cell functional capacity markers, anti-thyroglobulin antibody levels, tumor mutation status, and other markers). The Chi-Square (or Fisher's Exact test) will be used to assess the association of categorical clinical data with categorical biomarker data. Time-to-event clinical data (PFS, OS) will be correlated with biomarker data using Kaplan-Meier methodology and Cox regression models. Logistic regression models will also be used to predict binary clinical data with baseline biomarker data. Finally, graphical methods and descriptive statistics will be used to summarize the data as well. Two-sided p-values < 0.05 will be considered statistically significant.

16.5 Adverse Event Stopping Rule:

- 16.51 Monitoring: The principal investigator and the study statistician will review the study periodically (at least twice a year) to identify accrual, toxicity, and any endpoint problems that might be developing. The trial is monitored continually by the study team who are notified of every grade 4 and 5 event in real time. The Mayo Clinic Cancer Center (MCCC) Data Safety Monitoring Board (DSMB) is responsible for reviewing accrual and safety data for this trial at least twice a year, based on reports provided by the MCCC Statistical Office.
- 16.52 Adverse Event Stopping Rule: The stopping rule specified below is based on the knowledge available at study development. We note that the Adverse Event Stopping Rule may be adjusted in the event of either (1) the study re-opening to accrual after any temporary suspension or (2) at any time during the conduct of the trial and in consideration of newly acquired information regarding the adverse event profile of the treatment(s) under investigation. The study team may also choose to suspend accrual because of unexpected adverse event profiles that have not crossed the specified rule below. We expect approximately 10% of patients to experience grade 4+ adverse events (at least possibly related to study medication). In this study, we will suspend accrual to allow for a full review of the data, if any of the following occur in each cohort separately:

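### Section 16.4 names only CR and confirmed response as measures of tumour response, which gives its marker analyses little power in cohorts of 25; adding percent tumour change as a continuous outcome is a cheap improvement.

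*Combined protocol and SAP*

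**What the plan says.** Goals 2.31 to 2.37 each relate RECIST 1.1 tumour response to a marker; 2.32, for example, reads "To correlate tumor response (RECIST 1.1) with pretreatment PD-L1 and PD-L2 levels in the primary and/or metastatic tumor".

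Section 16.4 sets out the analysis. Its title, "Laboratory Correlative Studies (all done by Cohort", keeps the two cohorts apart. Its list of outcomes is "Clinical data (i.e. CR rates confirmed response rates, PFS, OS, etc.) will be correlated with tumor marker data of interest". The methods depend on the type of outcome:

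- For categorical pairs, chi-square or Fisher's exact test "will be used to assess the association of categorical clinical data with categorical biomarker data". No cut-point is given for turning a continuous marker into categories.
- "Logistic regression models will also be used to predict binary clinical data with baseline biomarker data". Nothing requires the marker to be split, and the test of the coefficient is not named.
- PFS and OS are related to markers by Kaplan-Meier and Cox models.

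The threshold is stated: "Two-sided p-values < 0.05 will be considered statistically significant". The section calls the work descriptive and meant to generate hypotheses, and claims no power. Section 16.2 sets 25 evaluable patients per cohort.

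Section 11.41 has the baseline sum of target dimensions (BSD) reported. The later sum likewise "will be calculated and reported as the post-baseline sum of dimensions (PBSD". Section 16.4 does not name percent change between the two as an outcome.

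**The concern.** The goals ask whether markers track tumour response. The response measures named for answering this are binary, and in Cohort 1 one of them is rare by design: Section 16.12 contrasts CR rates of 2% and 15%, which is 0.5 to 3.75 expected CRs among 25 patients. Cohort 1 can be declared positive on 2 CRs (Section 16.131), a count too small to say much about any marker.

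Mandatory archival tissue, mandatory blood and optional biopsies are collected for these questions. If response enters only as a binary outcome, a real association may well be missed. Because Section 16.4 sets a significance threshold, such a result could be reported as no association.

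**Working it through.** **The plan's own figure.** For Cohort 1 (n=25, success at 2 or more CRs), the exact binomial gives P(X≥2) = 0.0886 at 2% and 0.907 at 15%. These match the stated 0.09 and 91%. No power is stated for the correlative analyses.

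**Smallest p-value on a median split.** No cut-point is specified, so a 12/13 split of 25 is an assumption. With all k CRs in the group of 12, the two-sided Fisher p is C(12,k)/C(25,k). The opposite extreme, C(13,k)/C(25,k), is more probable and so is not added.

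- k=2: 66/300 = 0.22. Uncorrected chi-square p = 0.125.
- k=3: 220/2300 = 0.096. Chi-square p = 0.055.
- k=4: 495/12650 = 0.039. If all 4 fall in the group of 13, Fisher gives 0.057 + 0.039 = 0.096.

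**Chance of 3 or fewer CRs in 25.** At 15%, P(0) to P(3) are 0.017, 0.076, 0.161 and 0.217, which sum to 0.471. At 8% (2 of 25, the success threshold) the chance is 0.865.

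**Without a median split.** Significance is attainable with few CRs. The smallest exact rank p-value is 2/C(25,2) = 2/300 = 0.0067 for 2 CRs and 2/2300 = 0.0009 for 3. Fisher with 3 CRs and a 9/16 cut gives 84/2300 = 0.037. The remaining question is power.

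**Power by simulation.** The marker M is standard normal and shrinkage is Y = ρM + √(1−ρ²)·e, with e standard normal. CR, or response, occurs when Y exceeds the quantile that gives the stated rate. The test is two-sided at 0.05 with n=25. The documents give no ρ; values of 0.4 to 0.6 are assumed. The response rates are the Cohort 2 target of 25% (Section 16.14) and 65%, from the 64.8% on lenvatinib alone (Section 1.6). Logistic regression uses the Wald test.

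| Analysis | ρ=0.4 | ρ=0.5 | ρ=0.6 |
|---|---|---|---|
| Spearman, unsplit marker, percent change | 45-48% | 68% | 86% |
| t-test, split marker, percent change | 35% | 52% | 70% |
| Logistic, unsplit marker, CR 8% | 2-3% | 4% | not run |
| Logistic, unsplit marker, CR 15% | 9% | 14-16% | not run |
| Fisher, split marker, CR 15% | 11% | 15% | 23% |
| Exact rank test, unsplit marker, CR 15% | 20% | 30% | 45% |
| Logistic, unsplit marker, response 25%-65% | not run | 29-41% | not run |
| Fisher, split marker, response 25%-65% | 16-18% | 25-28% | 39% |
| Exact rank test, unsplit marker, response 25%-65% | 28-31% | 41-46% | 57-63% |

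**Failure of the logistic model.** At an 8% CR rate and ρ=0.5, about 20% of data sets have no finite estimate. Of these, 0.92^25 = 12.4% have no CR at all; complete separation accounts for the other 8 points or so.

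**The case against.** The strongest defence is that Section 16.4 is broader than its CR analysis. Several stronger readings are tempting, and the documents do not support them.

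- **That only yes/no outcomes are planned.** PFS and OS are in the same list and are analysed by Cox models, which do not depend on CR counts. The open-ended list and the categorical tests also leave room for ordered best response. What stands is that PFS and OS are not the tumour response that goals 2.31 to 2.37 name.
- **That 2 or 3 CRs can never give p<0.05.** This holds only on a median split, which the plan does not specify. At the 15% rate there is also a 53% chance of 4 or more CRs, when even the split test can succeed.
- **That the whole power gap is due to percent change.** Part comes from keeping the marker continuous. With the marker split throughout, percent change has 52% at ρ=0.5. With it unsplit throughout, an exact rank test has 30% for CR at 15% and 41-46% for confirmed response. The very low logistic figures also reflect the Wald test; a likelihood-ratio test would score higher.
- **That percent change should replace RECIST response, or that the cohorts should be pooled.** The goals specify RECIST response, and the trial's hypothesis (Section 1.7) is about CR. Lenvatinib alone gave a 64.8% response rate, so shrinkage in Cohort 1 partly reflects lenvatinib. One cohort is lenvatinib-naïve and the other has progressed on it; nothing in the documents supports a common marker effect, and analysis by cohort is a stated choice.

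The exploratory label limits the consequences, and no primary or secondary conclusion is affected. It does not remove the case for a more efficient outcome that needs no new data.

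**Conclusion.** The point holds as a cheap improvement. For CR, the named methods have little power at n=25: 4% to 16% by ordinary logistic regression at CR rates of 8% to 15% and ρ=0.5, and 30% at a 15% rate even with a more favourable exact rank test. The rank correlation with percent change has about 68%. Against confirmed response the gain is real but smaller.

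The Fisher limits are exact, given a median split. The power figures rest on an assumed correlation, on normality, and on CR and response being upper tails of the same shrinkage variable. Percent change came out ahead at each correlation tried, but at ρ=0.4 it too has less than 50% power. A reader might infer that the planned correlative work cannot answer its question; the documents and the arithmetic support only that its named response measures are inefficient.

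**What to change.** In Section 16.4, for the goals that correlate markers with tumour response:

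1. Add best percent change of PBSD from BSD as a further, continuous response outcome, analysed within cohort by Spearman correlation or rank tests with markers kept continuous.
2. Rank patients who progress or die before a post-baseline scan as worst.
3. Use ordered best response (CR, PR, SD, PD) as a supporting analysis, since percent change ignores new and non-target lesions.
4. Keep the planned CR, confirmed response, PFS and OS analyses, but use Firth or exact logistic regression when events are few.
5. Treat any cohort-stratified pooled analysis as optional and exploratory.

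The cost is SAP wording and a little programming, with no new data. The downsides are one more exploratory outcome at an unadjusted 0.05 threshold, and that shrinkage in Cohort 1 partly reflects lenvatinib activity. Reports should say so.

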17.0 Pathology Considerations/Tissue Biospecimens

17.1 Tissue Biospecimen Submission

NOTE: Patients must have consented to submission of the optional tissue(s) listed in the following table.

NOTE: Please refer to study specific Laboratory Manual.

17.11 Summary Table of Tissue Biospecimens for This Protocol

Type of tissue biospecimen to submit	Mandatory or optional	When to submit	Reason for submission (background / methodology section)	Where to find specific details for biospecimen submission	Storage/Shipping conditions†
Formalin-fixed paraffin-embedded (FFPE) primary tumor tissue blocks (blocks preferred , OR 30 four-micron unstained slides; Cohorts 1 and 2)	Mandatory	≤60 days after registration	Correlative studies (Section 2.31-2.33)	Section 17.3	Room temperature / Standard shipping
Formalin-fixed paraffin-embedded (FFPE) involved lymph node tissue blocks (blocks preferred , OR 30 four-micron unstained slides; Cohorts 1 and 2)	Mandatory (if available)	≤60 days after registration	Correlative studies (Section 2.31-2.33)	Section 17.3	Room temperature / Standard shipping
Formalin-fixed paraffin-embedded (FFPE) tissue blocks from biopsy of metastatic or locoregional tumor recurrence (Cohort 1)	Optional*	≤60 days after registration	Correlative studies (Sections 2.31-2.33 and 2.37-2.38)	Section 17.3	Room temperature / Standard shipping
RNA ^{later} ®-preserved tissue biopsy from metastatic or locoregional tumor recurrence (Cohort 1)	Optional*	≤60 days after registration	Correlative studies (Section 2.37-2.38)	Section 17.3	Incubate the specimens in the RNA ^{later} ® reagent at 4°C overnight and ship on ice. For long-term storage, transfer to -20°C and ship on dry ice

* Collection of this tissue is optional for research purposes. If a patient is not willing to undergo this procedure, it does not cause the patient to be ineligible; however, collection of this tissue is **strongly encouraged** (anticipate collecting samples from 20 of 30 patients in Cohort 1).

† See separate lab manual for detailed instructions.

17.2 Paraffin Embedded Tissue Blocks/Slides and Frozen Biopsy Samples

- 17.21 Submit one formalin fixed paraffin-embedded (FFPE) tumor tissue block with largest amount of invasive tumor (at least 1 cm of tumor for cases of surgical resection) from the original surgery (Cohorts 1 and 2). In addition, if available, submit one FFPE block containing tumor-involved lymph node. Preferably, chose a lymph node with gross tumor involvement. An H&E slide will be generated from all FFPE samples at the lead study site, which is responsible for correlative studies, to permit quality assessment of each tissue block. Once the QA is completed, and the necessary slides are cut, the tissue block will be returned. If tissue blocks cannot be released, prepare 30 slides for each tissue using the provided slides in the kit for each patient (See Laboratory Manual). Slides should not be baked since these tissues will be used for molecular studies. Slides should be shipped with 24 hours of tissue cutting.
- 17.22 A core biopsy will be performed after the patient is registered onto the study, but prior to the start of treatment from 20 patients in Cohort 1 (see separate lab manual). Four passes will be obtained from tumor tissue in, but not limited to the neck, chest abdomen, pelvis, bone or extremities. The first two passes will be formalin fixed and paraffin embedded (FFPE). The second two passes will be preserved in RNAlater® for future molecular analysis. An H&E slide will be generated from all samples at the University of Colorado, responsible for correlative studies, to permit quality assessment of the biopsies. (See Laboratory Manual)
- 17.23 The following materials below are mandatory (unless indicated otherwise) and required for shipment:
- Paraffin embedded tissue blocks preferred (OR 30 four-micron unstained slides from primary tumor and involved lymph node).
 - Specimen Submission: Tissue form
 - Surgical Pathology Report
 - Operative Report (*optional*)
- Note: Please include the ACCRU patient ID number on all materials listed above.**
- 17.24 The block/slides must be appropriately packed and shipped to prevent damage (see Appendix IV).
- 17.25 Tissue specimens must be shipped ≤ 60 days after registration.
- 17.26 Verify that the appropriate sections of the Archival FFPE Tissue Submission Form and/or Biopsy Specimen Acquisition Tracking Form are completed and filled in correctly. (These forms are located on the ACCRU web site in the “Manuals & Forms” folder.)

17.3 Study Methodology and Storage Information

- 17.31 Submitted tissue samples will be analyzed as detailed in Section 2.3. DNA extraction and storage of DNA for future pharmacogenetic assays (e.g., for genetic polymorphisms such as BRAFV600E, NRAS, HRAS, KRAS, mutation burden, etc., that may correlate with efficacy and tolerability. DNA will be isolated from 30 FFPE primary tumor samples and 20 core biopsy frozen samples from progressive tumors (Cohort 1). To broadly investigate mechanisms of response and resistance to combination therapy, we plan to generate gene expression profiles from the frozen biopsies (n=20) for analysis by RNA-Seq. Total RNA will be isolated with the RNeasy kit (Qiagen) and 500ng of RNA will be submitted to our Genomics and Microarray core facility for mRNA-seq library construction (TruSeq Stranded mRNA Library Kit, Illumina). We aim to collect at least 20 pre-treatment biopsies, depending upon tumor accessibility and patient consent. In parallel, we will also analyze the 30 FFPE primary tumor samples by RNA-Seq⁵¹. RNA will be generated from FFPE tissue sections (Qiagen FFPE All-Prep kit) and 100ng will be submitted for library construction (TruSeq Stranded RNA Access mRNA Library Kit, Illumina). We plan to sequence 60-80 million 1x125bp (FFPE) or 2x125bp (frozen) reads per sample. DNA and RNA will be analyzed for mutations using whole-exome sequencing technology in the University of Colorado Cancer Center Gene Expression Core facility led by [REDACTED]. Remaining DNA and RNA will be stored frozen at -80°C at the University of Colorado, according to patient consent information (see Section 6.12) until specific analyses are identified. As protocols are developed, they will be presented for ACCRU, ITOG, and IRB review and approval. (This collection is part of a general strategy of investigation for the majority of ACCRU studies.
- 17.32 At the completion of the study, any unused/remaining material will be stored in the University of Colorado Anschutz Medical Campus for future research according to the patient consent permission (see Section 6.15). Potential future research may include immunohistochemistry (IHC) analyses to analyze predictive biomarkers, changes in expression pattern with therapy, and correlation with response and/or adverse events. When a protocol is developed, it will be presented for ACCRU, ITOG and IRB review and approval.

